The intervention will be divided into three steps. At Step 1 for 3 months, the treatment arm will receive electronic monitoring (of participants' BP, weight, physical activity, food diary, and medication-taking) with weekly Interactive Technology Enhanced Coaching (ITEC) while the control arm will receive usual care with manual BP measurements monthly. At Step 2 for three months, the treatment arm will receive electronic monitoring with ITEC biweekly, and the control arm will receive electronic monitoring only. At Step 3 for three months, both the treatment arm and the control arm will receive electronic monitoring only.

Information from this study may be used to enhance self-care management, control blood pressure, and increase the quality of life for Black women who are burdened with the adverse effects of HTN and its high disability and mortality rates.

Our sample of n=45 participants per arm (N=90 in total), will be measured (electronic measurements, anthropometric measurements, and data collection tools) at baseline, 3 months, 6

months, and at 9 months post CDSMP. A hierarchical, mixed-effects repeated measures design will be used to analyze the data.

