## Fitbit Monitoring

With smart monitoring of connected devices in Fitbit Plus, data were tracked, analyzed, and transparently displayed to provide opportunities for participants to better understand their condition and self-manage by being actively engaged in their own care. In the CDSMP, all participants were taught to write action plans and report if they were successful, partially successful, or not successful in achieving their plan based on participant self-tracking of their data. Fitbit Plus allowed real-time adherence tracking. If participants were adhering to their action plan, study measures displayed a green color indicating a positive trend and if they were not adhering, measures would display a red color indicating a negative trend, alerting the PI to communicate with participants and encourage active engagement in their self-care.

Only the treatment arm action plans were monitored with individualized coaching messages (ITEC) via secure text messaging in the Fitbit Plus dashboard with real-time participant feedback. Coaching messages focused on helping participant's problem-solve barriers to goal

achievement with relevant dialogue to encourage BP control, medication adherence, and lifestyle modifications (physical activity, caloric intake, and weight management). The PI sent tailored ITEC messages via Fitbit Plus to treatment arm participants weekly for months 1-3, biweekly for months 4-6, and no ITEC messages for months 7-9 (to assess for sustainability).

During months 1-3, the control arm received usual care only, along with monthly manual BP and weight measures. After that time, the control arm was given the same wireless tools and apps as the treatment arm. In addition, they received individualized instruction equivalent to the treatment arm and practiced using the tools during a two-week trial period. For months 4-9, the control arm was monitored with IT via Fitbit Plus with no coaching. Fitbit Plus was used only to track participants for comparative data with the treatment arm. The control participants were not contacted between data collection periods, except to send reminders if they were not participating in daily measures.

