### Statistical Analysis Plan

**Sample size and power.** All participants meeting study eligibility requirements received the CDSMP classes for 6 weeks. Participants from this pool were randomized to the treatment arm (with ITEC and electronic devices such as the home BP monitoring, weight scale, and physical activity tracker), and the control arm, with IT monitoring only. Our sample of  $n=45$  participants per arm ( $N=90$  in total), measured at baseline, and at 3-, 6-, and 9-months post CDSMP, has approximately 80% power (assuming 5 dropouts per arm) to detect an effect size of  $\sim 0.205$  or greater at the  $\alpha=0.05$  level of statistical significance, given a realistic range of simulated unstructured covariance matrices. Assuming an 11% rate of attrition, the enrollment target was set at 90 for both arms, which would yield a final sample of 80 participants, or 40 per arm.

**Statistical analysis.** A hierarchical, mixed-effects repeated measures design was used to analyze the primary and secondary outcomes of interest. This model, which allows for heterogeneous variances across time points, is preferred over a simple univariate model that requires compound symmetry (i.e., the correlation between a measurement at time  $T_i$  and any other measurement within the same patients at  $T_j$ , is equal for all  $i$  and  $j$ ). A mixed-effects model is more efficient for handling missing at random (MAR) data than, for example, a generalized estimating equations (GEE) repeated measures approach, which requires the more restrictive assumption that missing data are missing completely at random (MCAR). We performed a sensitivity analysis using both a GEE model and sequential application of the EM algorithm to impute missing data. Data from participants ( $n=7$ ) who dropped out of the study before their first post-CDSMP visit were not included in the analysis. However, baseline information for these participants were compared with participants who continued in the study.

When appropriate a constrained longitudinal data analysis (cLDA) model was used, assuming the same baseline mean for treatment and referent arms with missing baseline data. The cLDA model examines treatment differences over time. Coffman et al. (2016) cite the cLDA as the method of choice for longitudinal RCTs because it yields robust estimates of treatment effect differences under reasonable missing data assumptions.

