Both models are valid for repeated measures if data are missing at random (MAR). Little's test was used to determine if variables were missing completely at random (MCAR) while significant covariate-dependent missing values were identified by regressing a dichotomous indicator variable for missingness against key models factors. (Li, 2013) That is, if the missing values were non-randomly associated with the latter variables of interest, the mechanism was deemed to be missing at random (MAR). A sampling of observed vs. non-unobserved items were subjectively scrutinized for signs of a 'missing not at random (MNAR)' pattern for the data. Overall, no relevant violation of the MAR assumption was evident in our analyses.

Descriptive statistics were used to summarize demographic data (such as marital status, education, and income) of study participants.

An independent (unpaired) samples t-test was used to determine the difference between the means of the treatment and referent groups. The dependent (paired) sample t-test was used to determine the mean differences between variables (systolic and diastolic BP and weight/BMI) for treatment and referent group participants from baseline (post-CDSMP) to month 3, from month 3 to 6, and from month 6 to 9. Time frames were allotted to further participant engagement in self-management.

The use of a two-sample t-test versus non-parametric methods for nonnormally distributed data has been debated in the literature (le Cessie et al., 2020). In general, the former is reasonable robust to departures from normality, providing that the sample sizes are sufficiently large, and the underlying variances are finite (with no extreme outliers) (Lumley et al., 2002)

All data collection tools (except the Hill-Bone CHBPTS medication subscale) were converted to a 100-point scale to enable comparison. Questionnaire scores were analyzed for changes across several time points using a mixed-effects repeated measures model for both groups. In comparison to a repeated measures ANOVA test, the mixed model tends to yield valid estimates of treatment effects even when the missing values are not completely missing at random (Detry & Ma, 2016). Rounding was based upon significant digits rather than a fixed number of decimal places (i.e., Goldilocks method) (Efird, 2021). Data were analyzed using SAS - v 9.4 (Cary, NC).

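### The only analysis the SAP ties to months 6 to 9 is a within-arm paired t-test; sustainability needs a named between-arm contrast from the mixed/cLDA model already planned

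*Combined protocol and SAP*

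**What the plan says.** Under Fitbit Monitoring, the treatment arm gets "no ITEC messages for months 7-9 (to assess for sustainability"). The Description of the Study keeps a concurrent randomised comparator in that period: "At Step 3 for three months, both the treatment arm and the control arm will receive electronic monitoring only".

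In the Statistical Analysis Plan, one method is attached to named intervals: "The dependent (paired) sample t-test was used to determine the mean differences between variables (systolic and diastolic BP and weight/BMI"), for treatment and referent participants, "from baseline (post-CDSMP) to month 3, from month 3 to 6, and from month 6 to 9".

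Three other methods are listed without a visit, interval or contrast:
- the main model: "A hierarchical, mixed-effects repeated measures design was used to analyze the primary and secondary outcomes of interest";
- a cLDA model, to be used when appropriate: "The cLDA model examines treatment differences over time";
- a two-sample test: "An independent (unpaired) samples t-test was used to determine the difference between the means of the treatment and referent groups".

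The SAP does not say which result answers the sustainability question, or how much of the effect must remain for it to count as sustained.

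**The concern.** Sustainability is a question about the ITEC effect, which is a difference between arms. A paired test in the ITEC arm answers another question: whether that arm's mean moved between month 6 and month 9. Two errors follow if it is used to judge sustainability.

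1. The month 6 to 9 change in one arm also contains whatever moves blood pressure or weight in everyone, such as season, changes in usual care or fading device use. A shared rise would look like loss of the coaching effect. A shared fall could hide a real loss.
2. Maintenance means no loss, so it would have to be read from a non-significant result. In an arm of about 40 women, that is weak evidence.

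The trial could then report the effect as lost when both arms drifted, or as kept when part of it had gone. The baseline-to-3 and 3-to-6 month paired tests have the same limit as evidence of an intervention effect.

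**Working it through.** **Inputs from the SAP.** Forty completers per arm, alpha 0.05 (taken as two-sided; the SAP does not say), visits at baseline and months 3, 6 and 9.

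**The plan's own figures.** Enrolment: 80 / (1 − 0.11) = 89.9, so 90, which agrees. The stated power of about 80% for an effect size of about 0.205 can be neither confirmed nor refuted, because the metric, the tested contrast and the simulated covariance matrices are not given. Read as a standardised difference at a single visit, it has 14.8% power with 40 per arm. Read as Cohen's f for the between-arm effect over four visits, it has 80% at a within-person correlation of 0.22. Nothing below depends on it.

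**Assumption.** The documents give no SD for blood pressure or for its change. Take a systolic SD of 12-15 mmHg and a month 6 to 9 correlation r of 0.5-0.7:
- SD of change = SD × √(2(1 − r))
- lowest: 12 × √0.6 = 9.3 mmHg; highest: 15 × √1 = 15.0 mmHg.

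**Paired test within one arm, n = 40 (noncentral t).** Detectable change at 80% power = 0.454 × SD of change: 0.454 × 9.3 = 4.2 and 0.454 × 15 = 6.8 mmHg.

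**Between-arm contrast of the month 6 to 9 change, 40 versus 40.** Detectable difference at 80% power = 0.634 × SD of change: 0.634 × 9.3 = 5.9 and 0.634 × 15 = 9.5 mmHg. The ratio is 0.634 / 0.454 = 1.4. The 95% CI half-width is 1.991 × √(2/40) × SD of change = 0.445 × SD of change.

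| SD of change (mmHg) | Paired test misses a true 4 mmHg loss | Paired test misses a true 7 mmHg loss | Paired test significant when both arms drift 4 mmHg | Half-width of between-arm CI (mmHg) |
|---|---|---|---|---|
| 10 | 31% | 1% | 69% | 4.5 |
| 12 | 46% | 5% | 54% | 5.3 |
| 15 | 62% | 18% | 38% | 6.7 |

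Under the same shared drift, the between-arm contrast is significant in 5% of trials.

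**Comparing the two paired tests with each other.** If both arms truly change by the same amount and each test has power p, the tests disagree with probability 2p(1 − p): 2 × 0.5 × 0.5 = 50% at p = 0.5, and 2 × 0.8 × 0.2 = 32% at p = 0.8. A finding of change in one arm and none in the other is therefore no evidence that the arms differ.

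**Sensitivity.** With 45 per arm, the paired multiplier falls from 0.454 to 0.427, about 6%. The figures are for systolic pressure; diastolic values would be lower if its SD is smaller.

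**The case against.** The strongest reply is that the plan already compares arms. The mixed model is the stated analysis for primary and secondary outcomes, the visits include month 9, the cLDA is described as a model of treatment differences over time, there is an unpaired test, and the Design section states a between-arm hypothesis. This stands. A reader might infer from the paired-test sentence that months 7-9 have no controlled analysis; the SAP does not support that. What is missing is a named contrast for sustainability.

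Nor does any section say that the paired test decides sustainability, or that a non-significant result will be read as maintained. That misreading is a risk the text leaves open, not a stated rule.

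A reader might also take low power as the reason to drop the paired test. It is not: the between-arm contrast is about 1.4 times less sensitive. The millimetre figures rest wholly on the assumed SD, and a true 7 mmHg loss is seldom missed unless the SD of change is near 15.

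Two further inferences should not be drawn:
- Regression to the mean after selection on an entry blood pressure does not explain change between months 6 and 9. Its size in the first interval depends on diastolic assumptions and on which baseline is meant, since the SAP calls it post-CDSMP while the Methods collect baseline data before the CDSMP.
- Controls were not contacted between data collection periods "except to send reminders if they were not participating in daily measures". The text is silent on reminders to the treatment arm in months 7-9. Silence does not contradict the statement that both arms had monitoring alone.

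**Conclusion.** The concern holds in a limited form. The period designed to test sustainability has one analysis assigned to it by interval, and that analysis leaves out the randomised comparator. It cannot separate loss of effect from shared drift, and its non-significance cannot show maintenance. The models that could answer the question are in the SAP, but no contrast from them is named for it.

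On the assumed SDs, a shared 4 mmHg drift would make the ITEC arm's paired test significant in 38-69% of trials, and a true 4 mmHg loss would be missed in 31-62% (SD of change 10-15 mmHg, 40 per arm). These illustrate the problem; they are not figures from the plan. That the paired test measures the wrong quantity does not depend on them.

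The between-arm contrast has its own limit. Under Fitbit Monitoring, the control arm received the devices only after month 3, so time on device differs between arms in months 7-9. The contrast removes only drift that the arms share.

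**What to change.** In the statistical analysis section, replace the paired t-tests as inferential evidence with two contrasts from the mixed/cLDA model:
1. the between-arm difference at month 9;
2. the change in the between-arm difference from month 6 to month 9.

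Report each with a 95% CI. Judge sustainability from both together, as how much of the month-6 difference remains. Do not judge it from a non-significant within-arm change, or from the month-9 interval excluding zero alone. For example, with a baseline-adjusted month-9 half-width of 3.8-5.8 mmHg (same assumptions), a difference that fell from 12 to 7 mmHg would still exclude zero (7 − 5.8 = 1.2) after losing 5 of 12 mmHg. Give the within-arm changes for all three intervals as descriptive means with CIs.

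The SAP is written in the past tense and already reports dropouts and missing-data findings, so it should also say when these contrasts were chosen.

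The cost is a change of wording and two contrasts from a model already planned; no new data are needed. The price is precision: on the assumed SDs, the 6-to-9 contrast detects 5.9-9.5 mmHg at 80% power where the paired test detects 4.2-6.8 mmHg, so a firm statement on sustainability becomes harder to make. The difference in time on device should be stated as a limitation beside the result.
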